Cover Page

Study Title

Prostatic Artery Embolization (PAE) for Treatment of Signs and Symptoms of Benign Prostatic Hyperplasia (BPH)

NCT:02026908

Last Reviewed by Northwestern University IRB 3/27/23

Protocol Version V 6.10.2019

Protocol Version 6.10.2019

Prostatic Artery Embolization (PAE) for Treatment of Signs and Symptoms of Benign Prostatic Hyperplasia (BPH)

STUDY SUMMARY

Title	Prostatic Artery Embolization (PAE) for Treatment of Signs and symptoms of Benign Prostatic Hyperplasia (BPH)
Short Title	PAE for BPH
Protocol Number	V 6.10.19
Phase	Pilot study
Methodology	Open labeled, non-randomized feasibility study
Study Duration	We estimate it will take approximately 4 years or 48 months to fully enroll and complete the study.
Study Center(s)	Single Center, Northwestern: (Northwestern University, Northwestern Memorial Hospital and Northwestern Memorial Faculty Foundation)
Objectives	Primary Objective: Evaluate the safety of PAE for the treatment of lower urinary tract symptoms (LUTS) attributed to BPH.
Number of Subjects	60
Diagnosis and Main Inclusion Criteria	Subjects with LUTS secondary to BPH refractory to/contraindicated for medical treatment
Study Product(s)	Embosphere Microspheres, Merit Medical, given intra-procedurally
Duration of administration	Dose given one-time during interventional radiology PAE procedure, given by and at the discretion of the interventional radiologist PI or Sub-l's
Statistical Methodology	Descriptive Statistics will be employed.

STUDY OBJECTIVES

Primary Objectives

Endpoint #1: Patient safety

The Primary Objective of this pilot study is to evaluate the safety of PAE for the treatment of LUTS attributed to BPH. Primary Safety Endpoints include:

1. A reduced incidence and severity of adverse events compared with historical TURP morbidity rates. These include genitourinary events (i.e., events associated with the urinary tract and/or the surrounding genital region)
2. Damage to the bladder floor, trigone, sphincters, and rectum

3. Incontinence as defined by International Continence Society (ICS) male IS score of at least +6 from baseline.
4. Infections
5. Secondary surgical interventions
6. All transient post-procedure events (i.e. *catheter dwelling time*)
7. Deaths

Endpoint #2: Objective clinical endpoints (measured at baseline, 4 weeks, 12 weeks, 6 and 12 months)

1. Change in International Prostate Symptom Score (IPSS)
2. Change in QoL bother question
3. Change in BPH impact index
4. Change in Qmax (*peak and total void volume at each follow-up visit*)

Secondary Objectives

1. Change in Post Void Residual (PVR) volumes:

Measure PVR at each follow-up visit to monitor impairment or improvement of bladder emptying due to the treatment or disease progression.

2. Change in Detrusor Muscle Pressure (Pdet) at Peak Urine Flow (Qmax)
3. Change in International Index of Erectile Function (IIEF-EF) domain:

Both BPH and many of its therapies adversely affect sexual function. Use validated, gender-specific measure of sexual function assessed at each follow-up visit.

4. Change in Male Sexual Health Questionnaire (MSHQ)
5. Change in Prostate volume: Many devices intended to treat BPH, such as TUMT, can reduce prostatic volume.
6. Cystoscopic appearance of the prostatic urethra

Endpoints

Preliminary Safety (Primary Endpoints) will be assessed during treatment and at post-treatment intervals of 1, 3, 6 and 12 months. Preliminary effectiveness (Secondary Endpoint) will be evaluated based on International Prostate System Score (IPSS) and cystoscopic visualization of the subject's urethra, prostate and bladder based on the timeline listed in the protocol.

Annual Long-term follow-up

Patients will be followed for up to 4 additional years after the 12-month visit (visit 6) for the following evaluations:

-physical examination including vital signs, weight and GU evaluation

- blood (comprehensive chemistry panel, PSA, Free PSA)
- laboratory evaluations
- urinalysis and urine culture to be done 1-2 weeks prior to cystoscopy and urodynamic testing at this visit
- PSA and free PSA
- DRE
- urodynamic testing including the same parameters as at baseline
- IPSS
- IIES
- MSHQ
- concomitant medications
- toxicity evaluation
- documentation of any new treatments for BPH and/or LUTS

Patients unwilling to come to clinic will be asked to complete the IPSS and IIEF questionnaires and provide information of any new treatments for BPH and/or LUTS by telephone, email or mail. Information on medications and adverse events will not be captured during the long-term follow-up period following the 12-month visit.

Study Design

Overall Clinical Study Design

This pilot study will be a single center, open labeled, non-randomized feasibility study to evaluate the initial safety of the PAE for the treatment of symptomatic BOO. 60 adult male subjects will be enrolled in this study.

All investigators and sub-investigators participating in this study have signed the Investigator Signature Page document. No additional investigators will be added until this agreement is signed. A new agreement will be signed by each investigator for every new version of the protocol created and approved by the IRB.

The first 10 subjects of this study will receive PAE adjusted by the investigators for volume and dose. These subjects will be treated under Monitored Anesthesia Care (MAC) anesthesia to ensure the investigator's complete control and to reduce implementation variables. The investigator will utilize real-time angiogram images of the prostate to direct the placement/movement of the microspheres throughout the targeted prostate treatment volume. These first 10 subjects will be carefully monitored for adverse events to establish preliminary safety of initial dosing plan. Once safety of the technique is established after the first 10 patients, MAC will only be used when medically necessary.

STATISTICAL ANALYSIS

General Considerations

General considerations: continuous variables will be summarized as n, mean, standard deviation, median, minimum and maximum. Categorical variables will be summarized as the number and percentage of patients in each category

Sample Size and Accrual

This is a single center pilot proof of concept study aiming to evaluate the safety, efficacy, and tolerability of PAE for the treatment of signs and symptoms BPH. A small number of subjects will be recruited for this purpose (50 subjects). The first 10 subjects will receive PAE adjusted for volume and dose. They will be carefully monitored for adverse events to establish preliminary safety of initial dosing plan. We estimate it will take approximately years to recruit, treat, and complete follow up on 60 subjects.

No large randomized studies using PAE to treat BPH have been done to date. The sample size has been chosen to evaluate PAE using a US population. The results of the study will provide critical preliminary data to later guide in powering a more statistically robust, and larger randomized controlled trial in the future.

Demographic and Baseline Characteristics

-age, gender, race, ethnicity

-baseline BPH/LUTS characteristics (prostate volume), PSA, free PSA, maximum flow rate (Qmax), average flow rate, detrusor muscle pressure (Pdet), voided volume, total time of voiding and post void residual volume (PVR)

-concurrent medications

-prior BPH/LUTS therapy

Safety and Outcome Analysis

Clinical and outcome measures will be compared to baseline. These included IPSS, IIEF, urodynamic test changes and prostate volume.

Duration of Procedure

Parameters to be recorded include during of procedure, number of Embosphere vials used, radiation exposure, catheter/wire used and amount of contrast.

Peak Urine Flow (Qmax)

Peak urine flow (Qmax) from urodynamic assessments will be summarized comparing baseline to follow-up measurements.

Post void residual (PVR)

PVR from urodynamic assessments will be summarized comparing baseline to follow-up measurements.

Detrusor muscle pressure (Pdet)

Pdet from urodynamic assessments will be summarized comparing baseline to follow-up measurements.

International Index of Erectile Function (IIEF)

IIEF will be summarized comparing baseline to follow-up measurements. Each subscale (erectile function, orgasmic function, sexual desire, intercourse satisfaction, overall satisfaction). Each subscale will be summarized separately at each time point (visit).

Prostate Specific Antigen (PSA)

PSA will be summarized comparing baseline to measurements at each follow-up visit.

Additional Variables from Urodynamic Testing

Average flow rate, voided urine volume and total time of voiding from the urodynamic assessments will be summarized and compared to follow-up time points (visits).

Laboratory evaluations

Summary statistics for baseline and change from baseline will be summarized.

Vital signs

Summary statistics for baseline and change from baseline will be summarized.

Cystoscopy

Cystoscopy results will be summarized for baseline and all subsequent cystoscopies.

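### The MSHQ is left out of the remote questionnaire set for annual follow-up, so long-term MSHQ results would come only from patients who choose to attend clinic

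*Combined protocol and SAP*

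**What the plan says.** The section Annual Long-term follow-up sets the period: "Patients will be followed for up to 4 additional years after the 12-month visit (visit 6) for the following evaluations". The list beneath it includes "urodynamic testing including the same parameters as at baseline", the IPSS, the erectile function questionnaire (printed there as IIES, read here as the IIEF) and the MSHQ.

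The same section then gives a reduced set for those who decline the visit: "Patients unwilling to come to clinic will be asked to complete the IPSS and IIEF questionnaires" and to "provide information of any new treatments for BPH and/or LUTS by telephone, email or mail". The MSHQ is not in it. Change in MSHQ is item 4 under Secondary Objectives.

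On analysis, Safety and Outcome Analysis says that clinical and outcome measures will be compared with baseline: "These included IPSS, IIEF, urodynamic test changes and prostate volume". For flow it says "Peak urine flow (Qmax) from urodynamic assessments will be summarized comparing baseline to follow-up measurements", with parallel wording for PVR and Pdet. The MSHQ is not named and has no paragraph of its own. General Considerations includes n in the summary of every continuous variable.

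**The concern.** Two of the three annual questionnaires are offered remotely and the third is not, and the text gives no reason for the difference. Entry to the remote set depends on the patient's own willingness to attend, and the visit being declined includes urodynamic testing. That willingness may be related to outcome in either direction: men who are doing well may see no reason to come, and men who did badly may have gone elsewhere.

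At one annual time point, IPSS and IIEF would then describe a wider group than the MSHQ, Qmax, Pdet and PVR. If erectile function and MSHQ results diverged in years 2 to 5, a reader could not tell a treatment effect from a change in who was measured. An MSHQ answer that was never requested may not be recoverable later.

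**Working it through.** The plan gives no attendance rate, SD or attender difference, so there is no figure to reproduce. The check has two parts.

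**1. Who can supply each annual measure**

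| Measure | Annual clinic list | Remote set | Source of long-term data |
|---|---|---|---|
| IPSS | yes | yes | attenders + remote responders |
| IIEF | yes | yes | attenders + remote responders |
| New BPH/LUTS treatments | yes | yes | attenders + remote responders |
| MSHQ | yes | no | attenders only |
| Urodynamics (Qmax, Pdet, PVR) | yes | no | attenders only |

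PSA, laboratory tests, vital signs and DRE are also clinic-only. Of the attender-only measures, the MSHQ is the only one that is a questionnaire.

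**2. Illustration of scale (all rates and differences assumed)**

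Let f be the share attending and d the attender minus non-attender difference in SD units. The cohort mean is f × (attender mean) + (1 − f) × (non-attender mean), so the attender mean is off from the cohort mean by

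(1 − f) × d.

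N is 60 in the Study Summary and Overall Clinical Study Design. Sample Size and Accrual gives both 50 and 60, so both are shown.

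| f | Attenders, N = 60 | Attenders, N = 50 | d = 0.2 | d = 0.5 | d = 0.8 |
|---|---|---|---|---|---|
| 90% | 54 | 45 | 0.02 | 0.05 | 0.08 |
| 70% | 42 | 35 | 0.06 | 0.15 | 0.24 |
| 50% | 30 | 25 | 0.10 | 0.25 | 0.40 |
| 30% | 18 | 15 | 0.14 | 0.35 | 0.56 |

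The shift does not depend on N. For comparison, the 95% half-width of a mean is 1.96/√n: 1.96/√30 = 0.36 SD with 30 attenders and 1.96/√18 = 0.46 SD with 18. In the table, the shift exceeds the half-width only for d = 0.8 with attendance of 50% or lower.

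**3. What adding the MSHQ would do**

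If a share g of non-attenders answers remotely, and those who answer are typical of non-attenders, the shift becomes

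d × f(1 − f)(1 − g) / [f + (1 − f)g].

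At g = 0 this is (1 − f)d, as above. At g = 1 it is zero. With f = 0.5, d = 0.5 and an assumed g = 0.5, it is 0.5 × 0.5 × 0.5 × 0.5 / 0.75 = 0.0625/0.75 = 0.08 SD, against 0.25 SD without the remote MSHQ. Adding the questionnaire therefore reduces the selection and removes it only if every non-attender replies.

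**The case against.** The strongest case against is that this is a single-arm pilot with descriptive statistics, whose safety endpoints and Endpoint #2 measures run to 12 months. A short remote set for patients who have already declined a visit is a reasonable compromise, and urodynamics cannot be done by mail. All of this stands, and it limits the point to low severity. It does not explain why the MSHQ was left out when two other questionnaires were kept.

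A reader might infer more than the documents support:

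- **That non-attenders give only symptom and erectile scores.** They are also asked about new treatments, which is the item most likely to reveal men who failed and were treated elsewhere.
- **That attender results will be presented as if they were the whole cohort.** The plan does not say so. Summaries carry n, and Safety and Outcome Analysis does not mention the annual visits or name the MSHQ. That this secondary objective has no written analysis is a separate gap.
- **That baseline will be unmatched.** The endpoints are worded as changes and the analysis section refers to urodynamic changes, so within-patient change is a natural reading. It is simply not spelled out.
- **That the QoL bother question and the entry "Change in BPH impact index" were dropped by mistake.** Endpoint #2 schedules both only to 12 months, so their absence from later years is consistent with the protocol.
- **That IPSS and urodynamics come from different patients.** Attenders supply both; remote responders only enlarge the IPSS and IIEF set.

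The comparison of attenders with remote responders can be made at analysis from data already planned. Only the MSHQ gap needs a change to data collection.

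**Conclusion.** The point holds in a narrow form. Following the plan as written restricts long-term MSHQ data to self-selected attenders, although the same patients are already being contacted for two other questionnaires. The urodynamic restriction is unavoidable, but the plan has no rule for showing its effect.

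The shifts of 0.02 to 0.56 SD rest entirely on assumed attendance (30% to 90%) and assumed attender differences (0.2 to 0.8 SD). They show that selection could matter, not that it will, and the direction is unknown. The 12-month endpoints are unaffected; only the descriptive data from years 2 to 5 are touched. This is a cheap improvement of low severity.

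**What to change.** 1. Add the MSHQ to the questionnaires requested by telephone, email or mail from patients who will not attend.
2. For the annual urodynamic measures, report the number attending each year, and report change in patients with both values against their own baseline. Pairing removes a mismatch in baseline sets; it does not remove selection of attenders.
3. Beside these results, tabulate 12-month IPSS and Qmax for attenders versus remote responders. This makes selection visible without correcting it.

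The cost is a slightly longer form for patients who have already declined a visit, and one extra table. Items 2 and 3 need no new data.

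### Event-type primary safety endpoints are summarized as number and percentage only, with no interval and no precision figure behind the sample size, although the first is worded as a reduction against historical TURP

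*Combined protocol and SAP*

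**What the plan says.** Study Objectives, Primary Objectives, Endpoint #1: "The Primary Objective of this pilot study is to evaluate the safety of PAE for the treatment of LUTS attributed to BPH". Seven items follow. The first is "A reduced incidence and severity of adverse events compared with historical TURP morbidity rates". The others are organ damage, incontinence defined by a score threshold, infections, secondary surgery, transient post-procedure events (catheter dwelling time is the example) and deaths.

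Study Summary, Statistical Methodology: "Descriptive Statistics will be employed".

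Statistical Analysis, General Considerations: "Categorical variables will be summarized as the number and percentage of patients in each category". Continuous variables get n, mean, standard deviation, median, minimum and maximum. The Safety and Outcome Analysis section then covers symptom and sexual-function scores, urodynamics, prostate volume, PSA, laboratory tests, vital signs and cystoscopy. It names no estimator for adverse events. No confidence interval, tolerable event rate or numerical TURP rate appears anywhere.

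Sample Size and Accrual gives two reasons for the number: "The sample size has been chosen to evaluate PAE using a US population", and the wish for preliminary data to help power a later randomized trial. Neither is a precision figure. The planned number is also inconsistent. Overall Clinical Study Design says "60 adult male subjects will be enrolled in this study". Sample Size and Accrual says "A small number of subjects will be recruited for this purpose (50 subjects" and then speaks of the time needed to "recruit, treat, and complete follow up on 60 subjects".

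**The concern.** The main result of this trial will be a short table of uncommon events in about 50 or 60 men. Printed as a count and a percentage, 0 (0%) or 3 (5%) shows nothing of how much higher the true rate could be. That matters more here than in a purely descriptive table, because the first endpoint is worded as a reduction against an external rate. A lower observed percentage is weak evidence of a lower true rate unless its uncertainty is shown. The same applies to data meant to guide the powering of a later trial: whoever plans that trial needs the range as well as the point.

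**Working it through.** **Inputs from the documents.** Planned number: 60 (Study Summary; Overall Clinical Study Design; Sample Size and Accrual) and 50 (Sample Size and Accrual). Early safety group: the first 10 subjects (Study Design; Sample Size and Accrual). Summary rule for events: n and % (General Considerations).

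**Assumptions.** The documents name no confidence level, so I use two-sided 95%, with one-sided 95% alongside for zero events. Each man counts once per event type, and all planned men are treated and evaluable unless stated.

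**Can the planned number be reproduced?** No. The plan gives no expected rate, precision target, level, power or dropout, so no formula leads to 60 or to 50.

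**Zero events.** The exact (Clopper-Pearson) upper limit is U = 1 − 0.025^(1/n) two-sided and 1 − 0.05^(1/n) one-sided.

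| n | Two-sided 95% upper limit | One-sided 95% upper limit |
|---|---|---|
| 60 | 1 − 0.025^(1/60) = 6.0% | 4.9% |
| 50 | 1 − 0.025^(1/50) = 7.1% | 5.8% |
| 10 | 1 − 0.025^(1/10) = 30.8% | 25.9% |

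If 10% or 20% of 60 were not evaluable (assumed; n = 54 or 48), the two-sided limit would be 6.6% or 7.4%.

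**One or more events.** The limits are the 2.5% quantile of Beta(x, n − x + 1) and the 97.5% quantile of Beta(x + 1, n − x). With n = 60:

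| Events | Observed | Exact two-sided 95% interval |
|---|---|---|
| 1 | 1.7% | 0.04% to 8.9% |
| 3 | 5.0% | 1.0% to 13.9% |
| 6 | 10.0% | 3.8% to 20.5% |
| 12 | 20.0% | 10.8% to 32.3% |

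At 3 of 60 the upper limit is 13.9/5.0 = 2.8 times the printed percentage.

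**Chance of seeing a harm at least once.** P = 1 − (1 − p)^n.

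| True rate | n = 60 | n = 50 |
|---|---|---|
| 1% | 1 − 0.99^60 = 45% | 39% |
| 2% | 70% | 64% |
| 3% | 84% | 78% |
| 5% | 1 − 0.95^60 = 95% | 92% |

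In the first 10 men, a harm with a true rate of 10% would not appear at all with probability 0.90^10 = 35%.

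**What this means for the TURP comparison.** Take 3 of 60 and treat the historical rate as a fixed number. Any TURP rate between 5.0% and 13.9% would look like a reduction on the percentages, yet it lies inside the interval for PAE. The plan gives no TURP rate, so I cannot say whether the relevant rates fall in that band.

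**The case against.** The best defence is that this is a declared pilot and feasibility study with descriptive statistics. It calls its safety findings preliminary, and any reader can compute an exact interval from n and %. Much of that stands. No estimate is biased, no test is invalidated and no data are lost. A descriptive pilot needs no power calculation. But an interval is itself a descriptive statement of precision, most useful when n is small, and an endpoint worded as a reduction goes beyond description.

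Four stronger readings are tempting, and the documents do not support them:

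- **The trial will declare PAE safe on a low or zero rate.** No decision rule for the full cohort is stated, so this is inference. The nearest text is in Study Design, which treats safety of the technique as something settled after the first 10 patients. That makes over-reading plausible but is not a rule for the final analysis.
- **The US setting is the sole reason for the sample size.** The plan also cites the lack of large randomized studies and the aim of informing a later trial. Both are legitimate pilot reasons; neither is a precision figure.
- **All primary safety results are n and % only.** Catheter dwelling time is a duration and would follow the rule for continuous variables. The point covers event-type items only.
- **The study is underpowered.** It proposes no test that could be underpowered.

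It is also fair to say that an interval alone does not complete the TURP comparison, because the plan names no TURP rate. That is a separate gap, and this point does not close it.

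**Conclusion.** The point holds for the event-type primary safety endpoints. The stated method, n and %, cannot by itself carry an endpoint worded as a lower incidence than TURP, and neither 50 nor 60 is tied to any statement of what it can exclude. Harms of several percent remain compatible with a clean record: up to 6.0% at 60 men and 7.1% at 50. These figures rest on an assumed two-sided 95% level and on full evaluability; with 10% to 20% loss from 60, the limit rises to 6.6% to 7.4%. The change is worth making because it concerns how the primary result will be read and costs almost nothing. It is an improvement to analysis and reporting, and does not invalidate the design.

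**What to change.** **General Considerations.** Add after the rule for categorical variables: *Each event-type primary safety proportion will be reported with its two-sided 95% Clopper-Pearson interval, over all men in whom PAE was attempted. Safety conclusions, including any comparison with historical TURP rates, will be worded on the interval and not on the point estimate alone.* The denominator needs stating because the documents define no analysis population, and a man is exposed to procedural risk once the procedure is attempted.

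**Sample Size and Accrual.** First reconcile 50 and 60. Then add, beside the existing rationale, the version that fits the final number:

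- At 60: *zero events excludes a true rate above 6.0% (two-sided 95%), and an event with a true rate of 5% is seen at least once with probability 95%.*
- At 50: the same sentence with 7.1% and 92%.

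If fewer men than planned have the procedure attempted, recompute the limits at the actual denominator.

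**Cost.** A few sentences and a line of code, with no new data and no change to procedures. The safety conclusion becomes more modest.

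### The planned sample size is given as 50 in one sentence and as 60 in three other places, with nothing to reconcile them

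*Combined protocol and SAP*

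**What the plan says.** The combined protocol and SAP gives the planned number of subjects in four places.

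- Study Summary table: the field "Number of Subjects" has the value 60.
- Study Design, Overall Clinical Study Design: "60 adult male subjects will be enrolled in this study".
- Statistical Analysis, Sample Size and Accrual, second sentence: "A small number of subjects will be recruited for this purpose (50 subjects".
- The same section, last sentence of the same paragraph: the time needed "to recruit, treat, and complete follow up on 60 subjects".

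Between the last two statements, the accrual paragraph also says: "The first 10 subjects will receive PAE adjusted for volume and dose". The one sentence on why this size was chosen is "The sample size has been chosen to evaluate PAE using a US population". The sentence after it adds that the results should inform the powering of a later randomized trial.

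**The concern.** The section whose job is to fix the target N gives two values within one paragraph, and only one of them agrees with the rest of the document. A reader cannot tell whether planned accrual is complete at 50 or at 60.

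N is a main planning figure in this single-arm pilot, which has safety as its primary objective and is meant to supply preliminary data for a larger trial. The number of subjects planned after the first 10, when the conditions of the procedure change, also depends on it. Because the plan contains no sample size calculation, the intended number cannot be recovered from anything else in the text.

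**Working it through.** **Can either figure be derived?** No. The documents give no alpha, power, effect size, standard deviation, event rate or dropout rate. The check is therefore a comparison of the four statements, followed by a test of the readings that might reconcile them.

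**Count.** Three statements give 60 and one gives 50. The difference is 10 subjects: 10/60 = 16.7%, or 10/50 = 20%.

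**Reading 1: 60 is 50 inflated for dropout.** Solving 50/(1 − d) = 60 gives d = 16.7%, and solving 50 × (1 + d) = 60 gives d = 20%. Neither rate is stated. The direction is also wrong: 50 is the number to be recruited, while 60 is the number to be recruited, treated and followed to completion.

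**Reading 2: 60 enrolled, 50 evaluable.** No such distinction is made, and the same reversal applies.

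**Reading 3: a lead-in of 10 plus 50 more.** The arithmetic works (10 + 50 = 60), but the text does not say it. The accrual paragraph mentions the first 10 directly after giving 50, without saying whether they are counted in it. The design section describes them as the first subjects of this study, which most naturally places them inside the total.

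**Stated rationale.** Studying a US population, or informing a later trial, supports neither number over the other.

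**Effect on precision (illustration only).** The plan specifies no confidence intervals. The calculations assume that every subject is evaluable, and the event rates used are assumptions, not figures from the documents.

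- Zero events, exact two-sided 95% upper limit = 1 − 0.025^(1/n)
- Observed rate of 10%: Clopper-Pearson 95% interval
- Mean change (such as IPSS), 95% half-width in SD units = t(0.975, n − 1)/√n
- Chance of seeing at least one event = 1 − (1 − p)^n for true rate p

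| Quantity | n = 60 | n = 50 |
|---|---|---|
| Zero-event upper limit | 5.96% | 7.11% |
| Interval at 10% observed | 3.76% to 20.51% (6/60) | 3.33% to 21.81% (5/50) |
| Half-width of a mean | 0.258 SD | 0.284 SD |
| At least one event, p = 1% | 45% | 39% |
| At least one event, p = 2% | 70% | 64% |
| At least one event, p = 5% | 95% | 92% |

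The ratio of half-widths is 0.2842/0.2583 = 1.10.

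**Subjects after the first 10.** These number 60 − 10 = 50 or 50 − 10 = 40. The zero-event upper limit in that group is 7.11% with 50 and 8.81% with 40.

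**The case against.** The strongest reply is that this hardly matters. The study is descriptive, and no test, threshold or numerical stopping rule uses N. The two statements that a reader would consult first, the summary field and the design section, agree on 60. Most readers would take 50 as a leftover. This stands as a limit on the consequence, but it does not remove the contradiction.

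Three further points are fair.

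- The precision figures describe quantities that the plan does not propose to report. They show the scale of the difference and nothing more. The only size that comes straight from the documents is 10 subjects.
- The lead-in reading is weak on the wording, and no separate analysis of subjects after the first 10 is planned. The reading is kept as a possibility because the text does not strictly exclude it.
- The protocol version dates from June 2019 and the last IRB review from March 2023. Enrolment status is not given, so the practical benefit of a correction now is uncertain.

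The accrual sentence lacks its number of years. That may come from text extraction or redaction, and nothing here rests on it. The 60 in that sentence is legible and is supported by two other places.

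**Conclusion.** The concern holds. The planned N is inconsistent by 10 subjects, and no text in the documents reconciles the two values. The likeliest reading is that 60 is intended, because three of the four statements give it, but this is an inference that only the sponsor can confirm.

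It is a consistency error in a figure the trial relies on, and it should be corrected. It does not threaten the analysis: on the assumptions above, the loss of precision in going from 60 to 50 is modest.

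**What to change.** State one planned N everywhere. By default, change 50 to 60 in the second sentence of Sample Size and Accrual. The sponsor may instead confirm one of two alternatives:

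- 50 is the target. Then correct the Study Summary, the Overall Clinical Study Design section and the last sentence of the accrual paragraph.
- The plan is 10 lead-in subjects followed by 50 more. Then say so in the accrual paragraph.

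The cost is one number, three places or one added clause, respectively. No extra patients, visits or analyses are needed. The administrative burden is that "A new agreement will be signed by each investigator for every new version of the protocol created and approved by the IRB". Making the correction together with the next amendment avoids a separate round of signatures.

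### Laboratory values and vital signs are summarised only as baseline and change, so the plan never reports how many men became newly abnormal, although safety is the primary objective

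*Combined protocol and SAP*

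**What the plan says.** In the combined protocol and SAP, the headings Laboratory evaluations and Vital signs under Safety and Outcome Analysis carry the same single sentence: "Summary statistics for baseline and change from baseline will be summarized". General Considerations, under Statistical Analysis, supplies the statistics: "continuous variables will be summarized as n, mean, standard deviation, median, minimum and maximum". It also says "Categorical variables will be summarized as the number and percentage of patients in each category", but no category of laboratory result or vital sign is defined anywhere in the text. There is no reference-range count, shift table, toxicity grade or threshold.

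The Study Summary gives the primary objective as "Evaluate the safety of PAE for the treatment of lower urinary tract symptoms (LUTS) attributed to BPH". Endpoint #1 under Primary Objectives lists seven safety items, the first being "A reduced incidence and severity of adverse events compared with historical TURP morbidity rates". Laboratory values and vital signs are not named among the seven.

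Annual Long-term follow-up lists a chemistry panel, PSA and vital signs for up to four years after month 12. It also lists a toxicity evaluation, yet it ends by saying that adverse events are not captured in that period.

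**The concern.** Laboratory harm usually falls on a few men and leaves the rest unchanged. The safety question is then how many men went from normal to abnormal, and the planned output does not answer it.

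- The mean and median describe the group, and a few affected men barely move them.
- The minimum and maximum describe one man at each end. They do not say whether he was the only one.
- Baseline and change are summarised separately. The man with the largest change need not be the man with the highest baseline, so the tables do not show whether anyone crossed a limit or was already beyond it.
- The laboratory sentence names no time point, whereas PSA and IIEF are to be summarised at each visit. A worst post-baseline value is therefore not assured.

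The study is meant to supply preliminary data for a larger randomised trial. For safety planning, such a trial needs proportions of men affected, and mean changes do not supply them.

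**Working it through.** The plan states no figure to reproduce. The sample size has no event rate, SD or power behind it, and no laboratory limit is given. The check is therefore an illustration.

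**Inputs.** N = 60 is from Overall Clinical Study Design ("60 adult male subjects will be enrolled in this study"). Sample Size and Accrual also gives 50, so both are shown. Everything else is assumed: an analyte in mg/dL whose changes are normal with mean 0 and SD 0.15; k men with an added rise of 1.0; all men normal at baseline, with a later value; and each affected man crossing the limit.

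**Mean change** = k × 1.0 / N.
- N = 60: k = 1 gives 0.017, k = 2 gives 0.033, k = 3 gives 0.050, k = 4 gives 0.067 mg/dL.
- N = 50: k = 3 gives 0.060 mg/dL.

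**SD of change** ≈ √[0.15² + 1.0² × (k/N)(1 − k/N)].
- N = 60, k = 3: √(0.0225 + 0.0475) = 0.26, or about 0.27 with the N − 1 divisor.
- N = 60, k = 1: √(0.0225 + 0.0164) = 0.20.
- For k = 3 the mean is 0.05 / (0.27/√60) ≈ 1.4 to 1.5 standard errors from zero. The median moves by about 0.01.

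**Maximum change** (100,000 simulated samples, N = 60).
- No affected man: about 0.34.
- One affected man: about 1.00. He is almost always the maximum, so a 95% range is roughly 1.0 ± 1.96 × 0.15 = 0.71 to 1.29.
- Three affected men: about 1.12, with 95% of samples between 0.92 and 1.36.

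The maximum separates none from some, but the ranges for one and three affected men overlap widely.

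**Count**, with exact (Clopper-Pearson) limits: lower = 0.025 quantile of Beta(k, N − k + 1), upper = 0.975 quantile of Beta(k + 1, N − k). For k = 0 the upper limit is 1 − 0.025^(1/N).

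| Men newly abnormal | N = 60 | N = 50 |
|---|---|---|
| 0 | 0%, upper limit 6.0% | 0%, upper limit 7.1% |
| 1 | 1.7% (0.0 to 8.9) | 2.0% (0.1 to 10.6) |
| 2 | 3.3% (0.4 to 11.5) | 4.0% (0.5 to 13.7) |
| 3 | 5.0% (1.0 to 13.9) | 6.0% (1.3 to 16.5) |

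**Smaller shifts.** The assumed rise is 1.0/0.15 ≈ 6.7 SD, which favours the maximum. In SD units with N = 60, one man shifted by 3 SD moves the mean by 3/60 = 0.05 SD and gives a typical maximum of about 3.1 SD, against 2.3 SD with nobody shifted. He is the maximum in 74% of samples. With a 4 SD shift the maximum is about 4.0 SD and he is the maximum in 94%. Three men shifted by 3 SD move the mean by 0.15 SD, with a maximum of about 3.8 SD.

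**The case against.** A reader might infer that the plan averages harm away, so that a report could declare no change in laboratory values while several men were affected. The documents do not support that. General Considerations also commits to the SD, minimum and maximum. In the illustration the SD rises from 0.15 to about 0.27 and the maximum from about 0.34 to about 1.1, so a fair reader would see that something had happened. What these figures do not give is the number of men or their baseline status.

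It can also be said that the safety objective rests on adverse events and that an important laboratory abnormality could be recorded as one. Up to month 12 that is possible. But the text states no rule for when an abnormal result becomes an adverse event, and Safety and Outcome Analysis has no adverse-event heading. After month 12 the plan says adverse events are not captured. That sentence follows the one on men who do not attend clinic and may be meant only for them, but it does not say so.

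The general rule for categorical variables could cover a normal/abnormal flag, but none is defined.

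Two limits on the point stand. The only itemised chemistry panel in the text is at the annual visits, and the schedule up to month 12 is not shown. It therefore cannot be assumed that any particular test is timed to detect an effect of the procedure or its contrast. And this is an open-label, descriptive pilot: the missing counts do not overturn any primary conclusion and can be produced from individual data.

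**Conclusion.** The point holds as a reporting gap. The stated analysis shows the most extreme laboratory or vital-sign change but not how many men became abnormal, nor whether the extreme man started abnormal. The stronger inference, that harm would be invisible, fails because the planned SD and maximum would usually signal it.

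Under the assumed figures, one and three affected men of 60 give typical maxima of about 1.0 and 1.1 mg/dL, and mean changes of 0.017 and 0.050. Counts would separate them as 1.7% and 5.0%, each with an exact interval. The analyte, SD and size of rise are assumptions. That no count or shift table is stated comes from the text itself. Choosing 50 or 60 subjects changes the percentages slightly and leaves the conclusion as it is.

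**What to change.** Keep the change summaries and add the following to Safety and Outcome Analysis before analysis.

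- **Laboratory tests.** For each test collected, give a shift table of baseline category (low, normal or high by the laboratory's reference range) against the worst post-baseline value and against each scheduled visit, including the annual follow-up visits. Report the number and percentage newly abnormal with an exact 95% CI, and state the denominator.
- **Vital signs.** Laboratory reference ranges do not apply. Report the number and percentage of men beyond limits that the sponsor specifies before analysis.
- **Annual Long-term follow-up.** Reconcile the listed toxicity evaluation with the statement that adverse events are not captured after month 12, so that it is clear which safety data exist for that period.

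The cost is a little extra programming on values the plan already summarises. Some crossings of a reference limit will be clinically trivial, and a large change within the range will not appear as a shift. The tables therefore supplement the change summaries and do not replace them.
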